All personnel involved with data collection have been trained in human subjects research protections and have up to date CITI certifications, specifically, the human subjects training for field workers (JHSPH Human Subjects Research Basic Course), and abbreviated Good Clinical Practice slide set (Good Clinical Practice, Social/Behavioral Interventions).

4. If the PI will not personally be on-site throughout the data collection process, provide details about PI site visits, the supervision over consent and data collection, and the communication plan between the PI and study team.

[name] aims to be on site throughout the data collection process of the FGDs and IDIs. When possible, [name] will travel to be present for Aim 3 data collection of surveys. However, in the

event that this is not possible, [name] will have regular conference calls with the local Research Program staff to monitor study progress and assure that the study is being implemented according to protocol. [name] will provide in-person oversight and monitor consent and data collection to ensure the study is progressing according to protocol.

B. Recordkeeping:

Describe how you plan to ensure that the study team follows the protocol and properly records and stores study data collection forms, IRB regulatory correspondence, and other study documentation. For assistance, contact: [contact]

[name] and [name] will be trained in study procedures and will oversee data collection and storage to ensure fidelity to the study protocol. [name] and/or [name] will discuss all concerns with the investigator team. [name] will be responsible for reporting to the IRB.

C. Safety Monitoring:

1. Describe how participant safety will be monitored as the study progresses, by whom, and how often. Will there be a medical monitor on site? If yes, who will serve in that role?

The PI assumes responsibility for the safety of study participants. Research Program staff will be trained to monitor for safety of study participants and report any concerns immediately to [name] and the PI. All Research Program staff will be trained in human subjects research and will be required to complete the CITI ethics module prior to any interaction with participants or study data. Certificates of human subjects completion will be kept on file at the Center for Indigenous Health's office in Baltimore.

We expect minimal risk. However, [name], a clinical psychologist, will be available if unexpected issues arise. Additionally, or if [name] is unavailable, local WMAT CHMWs who work on the WMAT Celebrating Life program (a program which provides support and referrals to people experiencing suicidal ideations or behaviors) will be available to provide support and referrals if needed.

In addition, field staff can enlist the Principal Investigator (PI), [name] [name], a Licensed Clinical Psychologist, to talk with the participant in person (if [name] is on site) or via phone and facilitate appropriate referrals for the participant if necessary. All research staff have the PI's cell phone number to contact her for these types of events 24 hours a day. All research staff also have [name] mentors, [name] and [name], cell phone numbers to serve as back-up should they be unable to reach the PI.

More specifically for Aim 3, The PI will meet with primary mentor, [name] (an expert in American Indian/Alaska Native mental/behavioral health research), co-mentor, [name] (an expert in American Indian/Alaska Native mental health and youth suicide prevention research and Licensed Psychologist), and Johns Hopkins Center for Indigenous Health Research Core Co-Leader and biostatistician, [name], on a monthly basis to review study progress and any issues related to study protocol, participant safety and confidentiality, and data safety. The PI will consult with [name], co-mentor, [name], and [name], community collaborator, on any serious adverse events within 48 hours of the event being reported. They along with [name] will also review any and all other unexpected adverse events at monthly executive meetings to ensure there are no concerning patterns.

2. If a Data Safety Monitoring Board (DSMB), or equivalent will be established, describe the following:

a. The DSMB membership, affiliation and expertise.

N/A

b. The charge or charter to the DSMB.

N/A

c. Plans for providing DSMB reports to the IRB.

N/A

3. Describe plans for interim analysis and stopping rules, if any.

D. **Reporting Unanticipated Problems/Adverse Events (AEs) to the IRB (all studies must complete this section):**

Describe your plan for reporting to the IRB and (if applicable) to the sponsor. Include your plan for government-mandated reporting of abuse or illegal activity.

The PI, with support from mentors [name] and [name], will assume responsibility of monitoring participants' safety, including reporting any serious and unexpected adverse events. Any adverse event that occurs will be categorized by Johns Hopkins staff as ranging from mild to serious. All adverse event reporting procedures, as designated by the Johns Hopkins IRB, will be followed by key study personnel with strict adherence.

If there is any suspected harm to self, others, or abuse reported during an interview, the Research Program staff will immediately report this information to the PIs. The PIs and the Local Study Staff Manager will report this to appropriate Tribal or Law Enforcement Authorities. With experience from previous studies with the White Mountain Apache community, the study team is knowledgeable of how to report this type of event without revealing study participation.

For Aim 3, Any adverse event that occurs will be categorized by Johns Hopkins staff as ranging from mild to serious. All adverse event reporting procedures, as designated by the Bloomberg School of Public Health IRB (BSPH IRB), will be followed by key study personnel with strict adherence. Serious Adverse Events (SAEs) include:

- Any death of a study participant
- A disability or incapacity which, in the opinion of the PI, causes substantial disruption of a study participant's ability to conduct normal life functions
- Hospitalization or extension of an existing hospitalization (excluding elective hospitalization for conditions unrelated to the study)
- Any intervention required to prevent one of the above outcomes

Serious and unexpected adverse events will be reported within three business days to BSPH IRB, tribal review entities, and the assigned NIH program officer. The PI, with guidance from mentors, will immediately report actions taken by any of these groups in response to adverse event reports to each of the other groups.

NOTE: The IRB does not require PROMPT reporting of all AEs, only those that are unanticipated, pose risk of harm to participants or others, and are related to the study. Anticipated AEs may be reported with the Progress Report.

E. Other IRBs/Ethics Review Boards:

If other IRBs will review the research, provide the name and contact information for each IRB/ethics review board and its Federal Wide Assurance, if it has one (available on OHRP's website at <http://www.hhs.gov/ohrp/assurances>). **For federally funded studies, subrecipient AND subrecipient's IRB MUST have a Federal Wide Assurance (FWA) number.**

Non-JHSPH IRB/REC	FWA Number

F. “Engaged” in Human Subjects Research:

For studies that involve collaboration with non-JHSPH institutions, complete the chart below by describing the collaboration and the roles and responsibilities of each partner, including the JHSPH investigator. This information helps us determine what IRB oversight is required for each party. Complete the chart for all multi-collaborator studies.

Insert collaborator names and FWA numbers, if available. Note who will be “engaged” in human subjects research by filling in the following table:

	JHSPH		
For federally funded studies, collaborators' FWA	00000287		
Primary Grant/Contract Recipient	BSPH Center for Indigenous Health (CIH)		
Grant/Contract Subrecipient	n/a		
Hiring Data Collectors	BSPH Center for Indigenous Health (CIH)		
Training Data Collectors	BSPH Center for Indigenous Health (CIH)		
Obtaining Informed Consent and/or Identifiable Data	BSPH Center for Indigenous Health (CIH)		
Accessing/Analyzing Identifiable Data	BSPH Center for Indigenous Health (CIH)		
Overseeing storage, access and use of biospecimens	n/a		

COMPLETE THE FOLLOWING SECTIONS WHEN RELEVANT TO YOUR STUDY:

XI. Secondary Data Analysis of Existing Data:

A. Study Design:

1. Describe your study design and methods. The study design must relate to your stated aims/objectives.

N/A

2. Provide an estimated sample size and an explanation for that number.

N/A

3. Provide a brief data analysis plan and a description of variables to be derived.

N/A

B. Participants:

1. Describe the subjects who provided the original data and the population from which they were drawn.

N/A

Note: If you are receiving, accessing, or using data from a U.S. health care provider, the need for HIPAA review is likely. If you plan to bring identifiable health information from a foreign country to a U.S. covered entity (e.g., lab at the Hopkins SOM), HIPAA may be triggered. If either of these conditions is met, check "yes" to the HIPAA question in the PHIRST application.

2. If you plan to analyze human specimens or genetic/genomic data, provide details about the source of those specimens and whether they were collected using an informed consent document. If yes, explain whether your proposed use is "consistent with" the scope of the original consent, if it potentially introduces new analyses beyond the scope of the original consent, and/or if it introduces new sensitive topics (HIV/STDs, mental health, addiction) or cultural/community issues that may be controversial.

N/A

3. Explain whether (and how) you plan to return results to the participants either individually or as a group.

N/A

XII. Oversight Plan for Student-Initiated Studies:

- A. For student-initiated studies, explain how the PI will monitor the student's adherence to the IRB-approved research plan, such as communication frequency and form, training, reporting requirements, and anticipated time frame for the research. Describe who will have direct oversight of the student for international studies if the PI will not personally be located at the study site, and their qualifications.

N/A

B. What is the data custody plan for student-initiated research? (Note: *Students may not take identifiable information with them when they leave the institution.*)

N/A

XIII. Creation of a Biospecimen Repository:

Explain the source of the biospecimens, if not described above, what kinds of specimens will be retained over time. Clarify whether the specimens will be obtained specifically for repository purposes or will be obtained as part of the core study and then retained in a repository.

N/A

A. Describe where the biospecimens will be stored and who will be responsible for them.

N/A

B. Describe how long the biospecimens will be stored, and what will happen at the end of that period.

N/A

C. Explain whether the biospecimens will be shared with other investigators, inside and outside of JHU, how the decision to share will be made, and by whom. Include your plans, if any, for commercial use. Also explain how downstream use of the specimen will be managed, and what will happen to left-over specimens.

N/A

D. Describe whether future research using the biospecimens will include specimen derivation and processing (cell lines, DNA/RNA, etc.), genomic analyses, or any other work which could increase risk to participants. Explain what additional protections will be provided to participants.

N/A

E. If future research could yield unanticipated incidental findings (e.g., an unexpected finding with potential health importance that is not one of the aims of the study) for a participant, do you intend to disclose those findings to the study participant? Please explain your position.

N/A

F. Explain whether the specimens will be identifiable, and if so, how they will be coded, who will have access to the code, and whether the biospecimens will be shared in linked (identifiable) form.

N/A

G. Explain whether the repository will have Certificate of Confidentiality protections.

N/A

H. Explain whether a participant will be able to withdraw consent to use a biospecimen, and how the repository will handle a consent withdrawal request.

N/A

I. Describe data and/or specimen use agreements that will be required of users. Provide a copy of any usage agreement that you plan to execute with investigators who obtain biospecimens from you.

N/A

XIV. Data Coordinating Center:

Complete if JHSPH serves as the Data Coordinating Center.

A. How will the study procedures be developed?

N/A

B. How will the study documents that require IRB approval at each local site be developed? Will there be some sort of steering or equivalent committee that will provide central review and approval of study documents, or will template consent forms, recruitment materials, data collection forms, etc. be developed by and provided to the local sites by the coordinating center without external review?

N/A

C. Will each local clinical site be overseen by its own IRB with an FWA, or will a Single IRB review the study? State whether the coordinating center will collect IRB approvals and renewals from the clinical centers; if not, explain why.

N/A

D. How will the coordinating center provide each local site with the most recent version of the protocol and other study documents? What will be the process for requesting that these updates be approved by local clinical center IRBs?

N/A

E. What is the plan for collecting data, managing the data, and protecting the data at the coordinating center?

N/A

F. What is the process for reporting and evaluating protocol events and deviations from the local sites? Who has overall responsibility for overseeing subject safety: the investigators at the recruitment site, the Coordinating Center, the Steering Committee, or a Data and Safety Monitoring Board (DSMB)? Is there a DSMB that will evaluate these reports and provide summaries of safety information to all the reviewing IRBs, including the coordinating center IRB? Please note that if there is a DSMB for the overall study, then the coordinating center PI does not have to report to the coordinating center IRB each individual adverse event/problem event that is submitted by the local site PIs.

N/A

G. Some FDA regulated studies have different AE reporting criteria than that required by the IRB (IRB Policy No. 103.06). How will you reconcile the different requirements, and who is responsible for this reconciliation?

N/A

H. Who is responsible for compliance with the study protocol and procedures and how will the compliance of the local sites be monitored and reviewed? How will issues with compliance be remedied?

N/A

XV. Drug Products, Vitamins, Food and Dietary Supplements:

Complete this section if your study involves a drug, botanical, food, dietary supplement or other product that will be applied, inhaled, ingested or otherwise absorbed by the study participants. If you will be administering drugs, please upload the product information.

A. List the name(s) of the study product(s), and the manufacturer/source of each product.

Name of Study Product	Manufacturer/Source
N/A	N/A

B. List each study product by name and indicate its approved/not approved status.

Approved by the FDA and Commercially Available	Approved by Another Gov't Entity (provide name)	Cleared for Use at Local Study Site
N/A	N/A	N/A

C. If your study product has an Investigational New Drug (IND) application through the U.S. Food and Drug Administration, provide the IND number, and the Investigators Brochure.

N/A

D. If your study product is a marketed drug, provide the package inserts or other product information. If the study product WILL NOT be used for its approved indication, dose, population, and route of administration, provide a detailed rationale justifying the off-label use of the study product.

N/A

E. If the study product does not require FDA approval (e.g., dietary supplements, botanicals, products not subject to the U.S. FDA, etc.), provide safety information (as applicable) and a certificate of analysis.

N/A

G. Explain who will be responsible for drug management and supply, labeling, dispensing, documentation and recordkeeping. Complete and upload into PHIRST the Drug Data Sheet available on the JHSPH IRB website at www.jhsph.edu/irb.

N/A

H. What drug monitoring and/or regulatory oversight will be provided as part of the study?

N/A

XVI. Medical Devices:

Complete this section if your study will involve an approved or investigational medical device (**diagnostic**, non-significant risk, significant risk).

N/A

A. List the name(s) of the study product(s), the manufacturer/source of each product, and whether or not it is powered (electric, battery). Provide product information. If it is electric, upload documentation of clinical engineering approval or its equivalent from a local authority, to ensure that the device is in good working order.

Name of Study Product	Manufacturer/Source	Powered?
N/A	N/A	N/A

B. List each study product by name and indicate its status as approved by a government authority or not approved.

Approved by the FDA and Commercially Available	Approved by Another Gov't Entity (provide name and approval information)	Not Approved
N/A	N/A	N/A

C. If your investigational device is Exempt from the FDA IDE regulations, explain which section of the code applies to your device and why it meets the criteria provided. If it is a **diagnostic device**, provide pre-clinical information about the sensitivity and specificity of the test and the anticipated failure rate. If you plan to provide the results to participants or their physicians, justify doing so, and explain how those results will validated (or not) against the current “gold standard”.

N/A

D. If you believe the investigational device is not IDE exempt under 21CFR 812.2(c), but is a “Non-Significant Risk” device considered to have an approved IDE application, provide information from the manufacturer supporting that position.

N/A

The overall goal of the analysis will be to assess for change in outcomes across time from all three survey timepoints (baseline, midline, and endline) using a pre/post analysis. All responses will be analyzed with SPSS software to examine internal consistency of each scale, item and scale level response distributions, inconsistencies in responses, and missing data patterns. Change over time in key outcomes (see table above listing outcomes) will be assessed. Session summary forms will be reviewed to assess intervention delivery fidelity and consistency across lessons. Cognitive interview responses will be compiled and analyzed to assess item fit and comprehension and to make potential improvements or changes to future surveys.

The original plan was to run an Observed Change Score Model where we created difference scores from baseline to midline and midline to endline and examined which predictors explained changes during those two periods.

After running these models using SEM, the models were unstable and therefore the results were biased and untrustworthy. Thus, I pivoted to conducting a Linear Mixed Model or Mixed Effects Model that could account for the repeated measures structure with only one group and allows participants to vary at baseline. Due to the number of participants in the data set, I wasn't confident that this model would run when first deciding on a model, but it ended up running without issue. I checked the assumptions for running the model with our data and all of the assumptions were met. The assumptions are:

Linearity: Check with residuals vs predictors.

Independence: Accounted for by random effects but plotted residuals over time to check.

Homoscedasticity: Plot residuals vs fitted values.

Normality of Residuals: Histogram and Q-Q plot of residuals.

Normality of Random Effects: Plot random intercept distribution.

The equation for the model is as follows

$$RFL = \beta_0 + \beta_1 Midline + \beta_2 Endline + \beta_3 AWOC + \beta_4 CCS + \beta_5 CCS ID + \beta_6 CES + \beta_7 LWI + \beta_8 IC + \beta_9 MMS + \beta_{10} RES + \beta_{11} SDI + u_i + e_{ij}$$

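### The replacement mixed model gives each predictor one pooled slope, which shows what explained change in RFL only under conditions the SAP does not state

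*Combined protocol and SAP*

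**What the plan says.** The Statistical Analysis Plan (Aim 3) describes two models in turn. Of the first it says "The original plan was to run an Observed Change Score Model where we created difference scores from baseline to midline and midline to endline". The aim of that model concerned each interval separately: the analysts "examined which predictors explained changes during those two periods". The SAP then reports that "After running these models using SEM, the models were unstable and therefore the results were biased and untrustworthy", without naming the failure. Next: "Thus, I pivoted to conducting a Linear Mixed Model or Mixed Effects Model", chosen because it handles repeated measures in one group and "allows participants to vary at baseline". The author had doubted at the outset that such a model would fit ("Due to the number of participants in the data set"), but "it ended up running without issue".

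The printed equation regresses RFL on Midline and Endline indicators and nine predictor terms (AWOC, CCS, CCS ID, CES, LWI, IC, MMS, RES, SDI), plus a child-level random term and a residual. The predictors carry no subscripts. The assumption list (linearity, independence, homoscedasticity, normal residuals, "Normality of Random Effects: Plot random intercept distribution") confirms a random intercept and mentions no random slope.

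The protocol's analysis paragraph (section V.C.4) asks for change in outcomes over the three surveys and names neither model. The measures table in V.C.1 schedules every scale except demographics at baseline (August 2023), midline (January 2024) and endline (May 2024). The only date in the available text, on the cover and beside protocol version 12, is 28 September 2023.

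**The concern.** The two models answer different questions. The difference-score model asked what goes with change, separately in each period. The mixed model asks what goes with RFL, pooled over waves. A non-zero pooled slope may mean only that children who score higher on one scale also score higher on RFL. A real within-child association can equally be understated. The checks the SAP lists are not designed to detect either.

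Aim 3 pilots the theoretical model to prepare a fully powered effectiveness study. If a pooled slope is read as evidence that a construct moves with RFL, the later study could be built around the wrong mechanism.

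**Working it through.** **Inputs.** From the SAP: T = 3 waves, two wave indicators, nine predictor terms, random intercept. From protocol III.B: up to 200 children, a feasibility figure. From the V.C.1 measure descriptions: alpha 0.84 for the self-esteem scale in earlier research. The documents give no ICCs, slopes or power calculation, so there is no plan figure to reproduce. The ICCs (0.3 to 0.7) and slopes below are assumptions.

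**1. What the equation contains.** Fixed effects: 1 intercept + 2 waves + 9 predictors = 12. The wave terms give mean RFL change, conditional on the predictors. No term lets a predictor slope differ by period or between and within children.

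**2. If predictors are time-varying.** Take one predictor, complete data, and let ICCy be the ICC of the outcome residual.

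- Between weight B = (T·ICCx + 1 − ICCx) / (1 − ICCy + T·ICCy)
- Within weight W = (T − 1)(1 − ICCx) / (1 − ICCy)
- Between share s = B/(B + W)
- Pooled slope = s × between slope + (1 − s) × within slope

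| ICCx, ICCy | B | W | s | within 0, between 0.5 | within 0.5, between 0 | both 0.5 |
|---|---|---|---|---|---|---|
| equal (0.5, 0.5) | 1.000 | 2.000 | 0.333 | 0.17 | 0.33 | 0.50 |
| 0.7, 0.3 | 1.500 | 0.857 | 0.636 | 0.32 | 0.18 | 0.50 |
| 0.3, 0.7 | 0.667 | 4.667 | 0.125 | 0.06 | 0.44 | 0.50 |

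A simulation with nine predictors (200 children, ICCs 0.5, predictor correlations 0, 0.3 and 0.5), with within slope 0 and between slope 0.5 for one of them, gave pooled slopes of 0.16 to 0.17 for that predictor. Its within-child slope, once split, was −0.01 to 0.00. So the other predictors do not remove the effect.

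**3. Constancy across periods.** Suppose RFL change follows predictor change with slope 0.5 in period 1 and 0 in period 2. With independent within-child deviations of variance v, the covariance sum is 0.5v and the deviation sum of squares is 2v, so even the split slope is 0.25. Period-specific regressions on predictor change give 0.50 and 0.00.

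**4. If predictors are baseline values.** Let a baseline predictor change RFL by g1 per unit in period 1 and g2 in period 2, with no association at baseline. Its cumulative effects at the three waves are 0, g1 and g1 + g2. The pooled slope is their mean, (2·g1 + g2)/3.

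- g1 = 0.3, g2 = −0.6: (0.6 − 0.6)/3 = 0.00
- g1 = 0.3, g2 = −0.3: (0.6 − 0.3)/3 = 0.10

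Simulation gave 0.00 and 0.10. The pooled slope describes average level, and the period pattern is lost.

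**5. Price of the alternatives.**

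- Fixed effects with a split: 3 + 18 = 21. With predictor-by-wave terms instead: 12 + 9 × 2 = 30.
- Standard error, split over pooled: 1/√(1 − s) = 1.22 at equal ICCs (1.07 to 1.66). A one-period change regression multiplies this by √2: 1.73 (1.51 to 2.35).
- Measurement error: treat 0.84 as reliability, so error variance is 1/0.84 − 1 = 0.19 per unit of true variance, and set both true slopes to 0.5. The within-child slope becomes 0.5(1 − ICCx)/(1 − ICCx + 0.19), that is 0.5 × 0.70/0.89 = 0.39 to 0.5 × 0.30/0.49 = 0.31. The pooled slope under the same error is about 0.41 (both ICCs 0.3) to 0.35 (both 0.7).

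**6. Dates.** A midline-to-endline difference needs endline data. On the planned schedule, 1 May 2024 is 216 days after 28 September 2023, and 1 January 2024 is 95 days after. The mixed-model text was therefore written after the cover date.

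**The case against.** The SAP never claims that its predictor slopes show what explained change; it says the approach was changed. The stated overall goal is change in outcomes over time, and the wave terms serve it for RFL. That stands, and it limits the point to the predictor slopes.

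The blending in step 2 requires time-varying predictors, and the SAP does not give their timing. That also stands. With baseline predictors the split cannot be fitted and step 4 applies instead, so the gap remains in another form.

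Nothing in the documents shows that within-child and between-child slopes differ here. With equal slopes the pooled model is undistorted, more precise and less attenuated by measurement error. A likelihood-based mixed model can also keep partial records, whereas change regressions need both waves. These are good reasons to keep the pooled model and add to it.

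A reader might infer from the cover date that a model chosen after seeing the data is being passed off as planned in September 2023. The documents do not support that. The SAP reports the switch openly, the date belongs to a combined file and matches the protocol version, and a separate SAP date may have been on a removed page. The SAP also implies that a mixed model was considered at the outset and set aside over sample size, so it is not clearly an invention after the fact.

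A reader might also take regression of change on change to be the abandoned analysis. The SAP does not say whether the predictors there were levels or differences.

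**Conclusion.** The point holds in a limited form. The model as printed cannot show which predictors explained RFL change in each period. If predictors are time-varying, the slopes match that question only when within-child and between-child slopes are equal and constant across periods, and the SAP neither states nor tests these conditions. If predictors are baseline values, no term represents their effect on change.

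The possible size is material: under the scenarios in step 2, a null within-child association could appear as 0.06 to 0.32, and a true 0.5 as 0.18 to 0.44. These figures rest on assumed ICCs and slopes, error-free predictors and complete data. They show what could happen, not that the fitted slopes are wrong.

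The SAP's reason for dropping the first model is also incomplete, because instability alone does not establish bias. That and the dating are documentation matters. Severity is modest.

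**What to change.** 1. State in the SAP whether each predictor enters as a baseline value or at every wave.
2. If time-varying, report beside the pooled model a version that splits each predictor into the child's mean and the deviation from it, and interpret only the within-child slope as relating to change. As a sensitivity analysis for constancy across periods, add period-specific change regressions, or interactions of the within-child deviation with wave.
3. If baseline, add predictor-by-wave terms.
4. In either case, do not describe the pooled slopes as predictors of change.
5. Housekeeping: give the SAP section its own date, label the mixed model as adopted after the change-score models were fitted, and name the failure seen (for example non-convergence or inadmissible estimates).

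The cost is some text and one or two extra results tables; no new data are needed if the surveys ran as scheduled. The statistical price is larger models in a data set whose size already worried the author, wider intervals, more attenuation from measurement error (step 5), and loss of children without both waves in the change regressions. The added results should therefore be presented as hypothesis-generating, and a within-child slope near zero should not be read as showing no association.
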